Blinding of the outcome assessors: It is a single blinded study, the outcome assessors only will be blind. The patients name will be sealed from pre and post records. Then two assessors will carry on, blindly and independently, the measurements and analysis of the study.

III) Data collection, management and analysis:

A] Data collection methods:

Primary outcome:

1. *Anterior teeth torque, extrusion/intrusion:* will be assessed by the principle investigator via CBCT taken before and after the completion of retraction. The principal investigator identified the landmarks, reference lines and planes, then interpreted the measurements in degrees and millimeters.

2. *Anterior teeth tip:* will be assessed by the principle investigator via CBCT taken before and after the completion of retraction.

Secondary outcomes:

1. *Root resorption:* will be assessed by the principle investigator via CBCT taken before and after the completion of retraction. The resorption will be identified using scoring system of Levander and Malmgren[21] that classifies it into 5 grades: 0: no root resorption; 1: mild resorption, with the root of normal length and only an irregular contour; 2: moderate resorption, with small areas of root loss and the apex having an almost straight contour; 3: severe resorption, with loss of almost one third of root length; and 4: extreme resorption, with loss of more than one third of the root length.

B] Data management:

A colleague outside the research team will enter the data and organize it in excel sheets in the computer of the orthodontic department.

Data will include all photographs, models and radiographs.

C] Statistical Analysis:

- The principle investigator will be responsible for the extraction of the required data from the CBCT taken before and after retraction. The data will be sent to a specialized statistician.

- The specialized statistician will be responsible for the statistical analysis of the study by:

1. Presenting the data as mean, standard deviation (SD) and Standard error (SE) values.

2. Using Paired t-test to compare between the friction and the frictionless group of retraction as well as to compare between the pre-and post -treatment data for each group.

3. Using Anova test to determine the rate of anterior segment retraction.

4. Statistically evaluate the patient acceptance for both techniques.

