- For this study, the specialized statistician used IBM11 SPSS12 Statistics Version 20 for Windows to perform the required statistics.

- The significance level will be $P \leq 0.05$. Highly significant variables are detected when P value is less than 0.01.

Assessors Reliability:

- To achieve high reliability for measurements, the supervisor will choose a well-experienced inter-examiner during the study.
- A training session will be provided for the examiners to ensure standard measurements techniques.
- Each examiner will complete the measurements on a model and will repeat the procedure after one week to assess the intra- and inter-examiner reliability.
- The supervisor will compare the measurements of the two assessors for disagreement with a difference of more than one millimeter.
- The supervisor will evaluate the amount of variation in measurements among and between examiners to test the performance of each assessor.
- The examiner with less reliability will receive additional training but will be replaced during the study.
- The specialized statistician will calibrate the intra and inter-examiner reliability for the measurements of the study by Inter-observer and intra-observer reliability will be assessed using $P \leq 0.05$.

IV) Method Monitoring:

A] Data Monitoring: An independent Data Monitoring Committee (DMC) will monitor the results of the study. The Committee will include the trial's supervisors, who will periodically review the trial data and identify the need for any adjustments or modifications during the study.

B] Interim Analysis: no interim analysis will be performed during the study.

C] Harm: The main operator will document and report any harms or unwanted effects during the study intervention to the trial supervisors. Also, any unpleasant experience will be reported by the patient in the final questionnaire at the end of the retraction. The main operator will be responsible for the management of any adverse effects or unfavorable side effects resulting from the appliance.

D] Auditing: The supervisor will follow up and review the different interventions and resulting data. And he will periodically follow up the trial progress including recruitment of patients, allocation of participants to study groups; adherence to interventions and reporting of harms. A meeting with the senior supervisor will be set every 3 months to monitor the progress of the study and the need for any adjustments.

V) Ethics and dissemination:

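### Reader reliability is to be judged by P ≤ 0.05, which does not measure agreement; the 1 mm limit cannot cover torque or resorption grade, and no intra-examiner repeat reading of CBCT is described

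*Combined protocol and SAP*

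**What the plan says.** All the reliability provisions stand under Assessors Reliability in section III of the combined protocol and SAP.

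- **Purpose.** "The specialized statistician will calibrate the intra and inter-examiner reliability for the measurements of the study". The same sentence then runs on, without a proper join, into the criterion: "Inter-observer and intra-observer reliability will be assessed using" P ≤ 0.05. No ICC, kappa, limits of agreement, measurement error or acceptance value is named there or elsewhere.
- **Numeric limit.** "The supervisor will compare the measurements of the two assessors for disagreement with a difference of more than one millimeter".
- **Repeat readings.** "Each examiner will complete the measurements on a model and will repeat the procedure after one week".
- **Other safeguards.** Examiners are trained, the supervisor reviews variation within and between them, and the less reliable examiner is to be retrained or replaced (the wording is unclear). None of these carries a statistic or a limit.

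The outcomes that reliability must cover are described under Data collection methods. Each is read on CBCT. For torque and vertical position the investigator sets landmarks, "then interpreted the measurements in degrees and millimeters". Root resorption uses a scoring system "that classifies it into 5 grades". The outcome table lists torque in degrees, and tip and vertical position in mm.

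On who reads the scans, the Blinding section says "Then two assessors will carry on, blindly and independently, the measurements and analysis of the study". Data collection methods says of each outcome that it "will be assessed by the principle investigator via CBCT taken before and after the completion of retraction".

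**The concern.** The primary outcome consists entirely of changes that a reader measures on CBCT, so the precision of those readings is part of the evidence. A reliability check has to show how far two readings of the same scan differ. A P value answers a different question: whether an association differs from zero, or whether a mean difference between readers can be detected. Judged by P, imprecise readings could be declared reliable, and close readings could be declared unreliable.

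The rest of the section does not fill the gap. The millimetre limit leaves one primary component (torque) and the secondary outcome (resorption) without any numeric limit. The described repeat is not on the imaging from which the outcomes come. And because two sections name different readers, it is unclear whose readings the check must cover.

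**Working it through.** **Inputs from the plan.** Criterion P ≤ 0.05 and disagreement limit 1 mm (Assessors Reliability); two-sided testing (Statistical Methods); 15 patients per group and planning difference 1.0 mm (Sample size calculation). The planning difference follows from the means cited there: 0.68 - (-0.32) = 1.00 mm. The plan gives no reliability coefficient or number of reading pairs, so there is no reliability figure to reproduce.

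**Assumptions.** Reading pairs n = 10, 15 or 30. The last is one pair per patient if both assessors read all 2 × 15 = 30 patients. The reader differences in reading B are illustrative.

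**Reading A: a coefficient tested against zero.**

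Smallest correlation reaching two-sided P = 0.05: r = t / √(n - 2 + t²), with t the 0.975 quantile on n - 2 degrees of freedom.

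Smallest consistency ICC for two readers: ICC = (F - 1) / (F + 1), with F the 0.975 quantile of F(n - 1, n - 1).

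| n | t | r | F | ICC |
|---|---|---|---|---|
| 10 | 2.306 | 0.63 | 4.026 | 0.60 |
| 15 | 2.160 | 0.51 | 2.979 | 0.50 |
| 30 | 2.048 | 0.36 | 2.101 | 0.36 |

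Example, n = 10: r = 2.306 / √(8 + 5.318) = 0.63; ICC = 3.026 / 5.026 = 0.60. The bar falls as pairs are added, so a larger check is easier to pass with worse agreement. Neither coefficient registers a constant offset between readers.

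**Reading B: a paired test between readers.**

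t = mean / (SD / √n) on n - 1 degrees of freedom; limits of agreement = mean ± 1.96 × SD.

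| Reader pair | Limits of agreement | P, n = 10 | P, n = 15 | P, n = 30 |
|---|---|---|---|---|
| Mean 0.2 mm, SD 1.0 mm | -1.76 to +2.16 mm | 0.54 | 0.45 | 0.28 |
| Mean 0.1 mm, SD 0.2 mm | -0.29 to +0.49 mm | 0.15 | 0.073 | 0.010 |

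The corresponding t values are 0.632, 0.775 and 1.095 for the first pair, and 1.581, 1.936 and 2.739 for the second. At every n the pair with the far wider disagreement has the larger P, so it looks the better of the two. The closer pair crosses 0.05 only at n = 30.

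**The 1 mm limit.** It is as large as the 1.0 mm difference the trial is planned to detect. It can be applied to tip and vertical position, which are listed in mm. It has no meaning for degrees or for an ordinal grade.

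**The repeat reading.** The repeat is on a model. Diagnosis (section I) and Data management (section III) list models apart from radiographs, so a dental model is the natural reading, though the term is not defined. Every outcome is read on CBCT, and no second CBCT reading by the same examiner is described.

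**The case against.** The strongest reply is that the criterion sentence is visibly broken and a method name may have dropped out. If an ICC was intended, with P only as its significance level, the coefficient itself could be reported. That is possible, and it would be wrong to infer that the trial report will show P values alone; nothing says so. What stands is that the current text names neither a statistic nor an acceptance value, and its one criterion fails under both usual readings.

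The section also contains more than P ≤ 0.05: training, a review of variation, retraining or replacement, and the 1 mm rule. These are real safeguards. But only the 1 mm rule is numeric, and it reaches only the mm outcomes.

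Three stronger readings are tempting and not supported.

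- A reader might infer that intra-examiner CBCT error will certainly be unknown. The plan says intra-examiner reliability is for the study's measurements, so a CBCT repeat may be intended; it is simply not described. Likewise, two independent assessors may well yield inter-observer CBCT pairs.
- A reader might infer that close agreement would usually be declared unreliable. In the example this happens at 30 pairs, not at 10 or 15, and only under the paired-test reading.
- A reader might infer a loss of power. The planning SD may already contain reading error, and the documents give no figure for that error.

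It can also be said that the choice of reader is a separate blinding issue. It is raised here only because a reliability check must cover the readings that are analysed.

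**Conclusion.** The concern holds. The plan's stated statistical criterion for reader reliability does not measure agreement. Under a test against zero it would accept correlations or consistency ICCs as low as 0.36 to 0.63, depending on the number of pairs. Under a paired test it ranks the two illustrative reader pairs the wrong way round at each size examined. Torque and resorption grade have no numeric limit, and the described intra-examiner repeat is not on CBCT.

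The coefficients rest on assumed numbers of pairs (10, 15, 30) and the paired-test results on illustrative reader differences. The absence of a named statistic, the unit mismatch and the conflict over who reads are plain from the text and need no assumption. The consequence concerns how far the measurements can be trusted and how their precision is reported; no effect on power or on the treatment comparison is claimed. The change should be made, and it is inexpensive.

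**What to change.** 1. Replace P ≤ 0.05 by a two-way absolute-agreement ICC with 95% CI, plus Bland-Altman limits of agreement or Dahlberg error, for each outcome in mm or degrees. Use weighted kappa for the resorption grade.
2. Compute inter-observer agreement from the two assessors' CBCT readings, and intra-observer agreement from one-week repeat readings of a subset of existing trial CBCT scans.
3. State disagreement limits in each outcome's own unit, including degrees for torque and grades for resorption, with values chosen by the team.
4. Reconcile Blinding with Data collection methods and Statistical Analysis, so that the readings analysed, and covered by the reliability check, are those of the blinded assessors already named.

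The team should also fix in advance the number of repeat scans, the acceptance levels, the kappa weights, the handling of several teeth per patient, and whether the ICC refers to single or averaged readings.

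The cost is SAP wording and a small number of repeat readings; no new scans. If in practice only the principal investigator would have read the scans, the two blinded assessors would each have to read up to 30 × 2 = 60 scans, which the Blinding section already implies.

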On the other hand, theories have suggested that the drawbacks encountered with the sliding mechanics for incisors retraction can be overcome by the use of well-designed loops providing a better control over the moment/ force ratio and thus the position of anterior teeth. However, minor errors in the loops design can result in major differences in tooth movement, and some patients may find the loops uncomfortable[9].

It is well known that the amount of tip, torque, extrusion/intrusion in anterior teeth is very critical as it affects the final aesthetic outcome. Accordingly,

anterior segment vertical and horizontal control is considered a primary concern to all orthodontists. Despite the large number of studies dealing with mechanics of space closure, little evidence has been found in the orthodontic literature regarding the best guidelines for anterior teeth position after anterior teeth retraction. Therefore, a recent systematic review has recommended additional studies to determine the best way for anterior segment retraction.[11]

There's scarcity in literature concerning the issue of anterior segment retraction technique and its effect on anterior teeth position. Therefore, a randomized clinical trial has been chosen to investigate this issue, aiming to support clinicians with the best guidelines for anterior segment retraction.

Review of Literature

It's widely accepted that one of the main goals seeking orthodontic treatment is aesthetic[12]. Aesthetics are mainly determined by controlling the position of the anterior teeth. Accordingly, three-dimensional control of anterior teeth during orthodontic treatment is important to avoid any side effects on the dentition which might happen due to the applied orthodontic mechanics. Several approaches have been implemented to control both the anteroposterior and the vertical positions of the incisors with multiple studies conducted to evaluate their effectiveness.

- The review of literature will be discussed under the following titles:
 1. Friction mechanics for anterior segment retraction.
 2. Frictionless mechanics for anterior segment retraction.
 3. Friction vs. frictionless.
 4. CBCT for evaluation and its reliability.

1) Friction mechanics for anterior segment retraction

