- The force will be measured by a force gauge and reactivated every 4 weeks maintaining constant force of retraction all over the retraction phase.

➤ **Follow up visits**

Patients will be asked to attend for follow up sessions every 4 weeks for:

- Evaluation mini-screws stability.
- Replacement of the power chain to maintain a force of 160 gm per side.
- Reactivation of the T-loop by further distal activation and cinch back if needed.

➤ **Criteria for discontinuing or modifying the allocated intervention:**

In cases of prolonged swelling or pain related to the mini-screw the patient will be given strict oral hygiene measures and the beginning of retraction will be postponed for three weeks.

In cases of loose or broken mini-screws, the screw will be removed and replaced.

➤ **Retraction records**

Following retraction of the anterior segment, patients will be referred to the same radiology center to acquire the final CBCT to assess the movement and inclination of anterior teeth.

➤ **Materials**

- American Orthodontics Brackets, Roth prescription, 0.022 slot size.
- American Orthodontics Elastomeric power chains.
- American Orthodontics Elastomeric O-ties.
- American Orthodontics Ligature wire.
- Mini-screw (1.6- by 8-mm, bracket head design; Dual Top Anchor System, Jeil Medical Corporation, Seoul, Korea).
- American Orthodontics Arch wires.
- American Orthodontics Molar bands/tubes.
- Crimpable hooks (Dentos Inc.)

D] Outcomes

[figure not shown]
Primary outcome: is to monitor the changes in the anterior teeth position (final anterior teeth tip, torque and vertical position) in association with each technique after retraction

Secondary outcomes: are to detect the presence of any root resorption associated with the different methods used for anterior segment. All outcomes

will be assessed as the difference between T0 at the start of anterior segment retraction after full canine retraction and T1 after complete space closure.

E] Participant timeline:

1. The principle investigator will screen the potential patients through careful clinical examination of patients at the orthodontic department, Faculty of Oral and Dental Medicine at The Future University of Egypt.
2. All recruited patients must fulfil the previously mentioned inclusion and exclusion criteria.
3. Every participant will be asked to sign an informed consent before the beginning of the study.

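### Patient-reported harm rests on one undescribed questionnaire at the end of retraction, with nothing planned for patients who stop early, so discomfort may be under-recorded

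*Combined protocol and SAP*

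**What the plan says.** The Harm section (IV, C) gives two routes for recording harm.

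- **Operator.** "The main operator will document and report any harms or unwanted effects during the study intervention to the trial supervisors". Under Auditing (IV, D), the supervisor's periodic follow-up covers "adherence to interventions and reporting of harms".
- **Patient.** In addition, "any unpleasant experience will be reported by the patient in the final questionnaire at the end of the retraction". No section describes the questionnaire's items, scale or recall period, or says who receives it if retraction is not finished.

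The section on follow-up visits opens "Patients will be asked to attend for follow up sessions every 4 weeks for" and lists three tasks: "Evaluation mini-screws stability", "Replacement of the power chain to maintain a force of 160 gm per side" and "Reactivation of the T-loop by further distal activation and cinch back if needed". Item 9 of the participant timeline adds impressions to the same visits. Neither place lists a question about symptoms. The section on discontinuing or modifying the intervention mentions pain only where it comes from the miniscrew, a device used in both arms.

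On loops, the introduction remarks that "some patients may find the loops uncomfortable". The Blinding section states that operators cannot be blinded, either when applying the interventions or at follow-up. Item 4 of the Statistical Analysis section (III, C) plans a statistical evaluation of patient acceptance of both techniques, without naming an instrument or time point.

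**The concern.** A questionnaire given once, when retraction ends, reaches only patients who get that far, and it asks them to recall the whole phase. A patient who leaves during retraction has no planned point at which her own account is collected. What remains is the operator's record. That record has no form, prompt, definition or grading, and the person keeping it knows which appliance the patient wears.

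One possible source of discomfort, the closing loop, belongs to one arm only. If discomfort contributed to early stopping, the patients with most to report would be missing from the patient-reported data, and possibly unequally between arms. The CBCT outcomes are a separate matter. At stake here is the only patient-reported information on harm and, if the same questionnaire feeds it, the planned comparison of acceptance. An account not taken when a patient leaves usually cannot be recovered later.

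**Working it through.** **1. Routes and timing side by side**

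| Route | When | Structured? | Reaches early stoppers? |
|---|---|---|---|
| Patient questionnaire (Harm) | Once, at end of retraction | Content not described | No provision stated |
| Operator record (Harm) | During the intervention | No form, prompt or grading | Yes, if the operator notes the complaint |
| 4-weekly visit tasks (Follow up visits; timeline item 9) | Every 4 weeks | Appliance tasks and impressions | No symptom question listed |
| Supervisor review (Auditing) | Periodic | Reviews what was reported | Only through the operator record |

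No row combines a patient's own report, a structured form and a time point before the end of retraction.

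**2. Room for loss in the plan**

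Inputs from the sample size section: difference 1.0 mm, SD 0.76, power 0.8, type I error 0.05. The test is two-sided (Statistical Methods) with 1:1 allocation (Study design).

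n per group = 2 × (1.960 + 0.842)² × 0.76² / 1.0² = 9.07, rounded up to 10.

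This reproduces the stated 10 per group. The noncentral t distribution gives power 0.795 at 10 per group, close to the stated 0.8.

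Allowance for loss: 15 − 10 = 5 per group, and 5/15 = 33.3%. The check in the other direction is 10 / (1 − 1/3) = 15.

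The allowance is for loss from all causes. Under Implementation, assignment takes place before levelling and alignment. Levelling, miniscrew placement, extraction and canine retraction all come before any retraction loop is fitted. An unknown share of the five could therefore leave before they are exposed to a loop.

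**3. What completer-only reporting could do (assumed figures)**

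The documents give no discomfort rate and no reasons for dropout. Assume that 15 patients in an arm start retraction and 6 have marked discomfort (6/15 = 40%), and that every one of k early stoppers is among those 6. The rate seen among completers is (6 − k) / (15 − k).

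| Early stoppers k | Completers with discomfort | Rate seen |
|---|---|---|
| 0 | 6/15 | 40% |
| 1 | 5/14 | 36% |
| 2 | 4/13 | 31% |
| 3 | 3/12 | 25% |
| 4 | 2/11 | 18% |
| 5 | 1/10 | 10% |

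The last row is an upper illustration. It spends the whole allowance on patients who stop after the loop is fitted and who all have discomfort.

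**4. Direction**

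If the stoppers are instead all free of discomfort, the rate seen is 6 / (15 − k). With five stoppers that is 6/10 = 60%, above the assumed true 40%. The direction of error depends on who stops, and the documents do not say.

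**The case against.** The strongest reply is that the plan does have a route during treatment, and that it comes first in the Harm section. The operator must document any harm throughout the intervention, patients attend every 4 weeks, and supervisors follow up the reporting. A patient who stops because the appliance hurts falls within that duty. This stands: her complaint can be recorded. Lack of blinding may bias a record, but it does not mean there is none. The route narrows the gap without closing it, because it is unprompted and is not the patient's own report.

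Several stronger readings are tempting, and the documents do not support them.

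- A reader might infer that early stoppers are never asked about discomfort. The text shows only that no such question is planned. The visit task list is not exhaustive, since the timeline adds impressions, and asking at a visit or at withdrawal is not excluded.
- A reader might infer that the protocol predicts loop discomfort. The introduction says only that some patients may experience it, as a background remark. The source cited there is, by its title, a typodont simulation.
- A reader might infer that discomfort will be undercounted, and more so in the loop arm. That needs early stopping linked to discomfort, and the documents give no such link or rate.
- A reader might infer that a patient whose loop is removed misses the questionnaire. It is tied to the end of retraction, not to completing the allocated appliance, so a patient who stays under treatment could still receive it.

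It is also true that no between-arm analysis of harms is specified and that acceptance is not linked to this questionnaire. The restriction to completers is therefore conditional on that use.

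**Conclusion.** The concern holds as a gap in data collection, not as a demonstrated bias. As written, the only planned patient report of harm is one undescribed questionnaire at the end of retraction, with no provision for patients who stop early. Until then, recording is unstructured and is done by an unblinded operator. Discomfort may be under-recorded, and a comparison of experience or acceptance based on this questionnaire would cover completers only.

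The size is unknown. Under the assumptions shown, an arm's rate of 40% would appear as anything from 40% (no stoppers) to 10% (five stoppers, the extreme case), and it could be overstated if those who stop are the comfortable ones. With 15 patients per arm, two affected stoppers are enough to move it from 40% to 31%. The sample size and the CBCT outcomes are not affected by this point. It is worth correcting before retraction begins, because the correction is cheap and the information is hard to recover afterwards.

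**What to change.** In both arms, give the same short discomfort form, completed by the patient:

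- at each 4-weekly retraction visit already scheduled;
- when a patient stops the allocated appliance for any reason, or leaves the study.

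Describe the form and the final questionnaire in the protocol (items, scale, recall period). State whether either one supplies the acceptance analysis in item 4 of the Statistical Analysis section. Report by arm the number who started retraction, the number assessed, and the proportion with any complaint among all who started. That denominator leaves out losses before any retraction appliance is fitted. Keep the operator's harm record as a second source and report it separately.

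The cost is one short form per visit and a little more data entry. It needs no extra visits, staff or procedures and no change in sample size. At a minimum, describe the existing questionnaire and offer it at early stopping. That would cover most early stoppers, but it would still leave completers to recall the whole phase.
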